Oficial title

Polypectomy With Hot vs Cold Snare in Small Colonic Lesions

• Valladolid (Spain), 17 November 2018

Abstract

Colonoscopy is the technique of choice for the diagnosis and prevention of colorectal cancer (CRC). The identification and extirpation of adenomas decreases the incidence of CRC by up to 76%. More than 70% of the excised lesions are less than 10 mm. There is controversy about the technique to be used (resection with cold vs hot snare) in the lesions of 5-9mm. Both use a polypectomy snare, differing in that the cold handle cuts by friction, while the hot snare uses electrical current. We propose a multicentre randomized clinical trial comparing both endoscopic techniques. At least 394 injuries per group will be included, randomizing patients to whom a diagnostic colonoscopy is requested for symptoms, screening or revision protocols. Randomization will be performed stratified by endoscopist. The primary objective is the proportion of incomplete polypectomies, which will be analyzed centrally from random biopsies of the edges of the lesion. As secondary objectives, we will compare the proportion of immediate and delayed hemorrhagic complications, the evolution of postprocedural abdominal pain and the factors associated with incomplete excision in each group and the factors associated with a failed cold polypectomy. The analysis of the primary objective will be carried out by means of the z test of homogeneity without using the correction of Yates, estimating the confidence interval of the difference between both groups. The analysis will be carried out by intention to treat and by protocol.

1. Introduction

Colorectal cancer (CRC) is a major cause of morbidity and mortality worldwide. It is estimated that in 2008, 1233,000 new cases were diagnosed and more than 600,000 people died for this reason throughout the world (1). Colonoscopy is the technique of choice for both diagnosis and prevention (2), since the identification and removal of colonic adenomas reduces the incidence of CRC by up to 76% (3-7).

Different endoscopic techniques have been developed for the removal of adenomas; The choice of some over others is made according to the size, morphology and location of the lesion.

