- $^{\fbox{2}}$ Evaluate the factors associated with an incomplete extirpation in each group.
- ² Evaluate the factors associated with a failed cold polypectomy.

4. Design

Randomized clinical trial comparing two endoscopic techniques.

5. Methods

Population to study

The study population includes patients scheduled to perform a colonoscopy in a non-urgent way. The patient will be invited to participate before performing the colonoscopy.

The variables defined in Annex 1 will be collected in a dissociated form database.

Inclusion and exclusion criteria

The inclusion criteria are:

• Patients older than 18 years scheduled to undergo a colonoscopy.

The exclusion criteria are:

- Absence of lesions of 5-9 mm.
- Contraindication for polypectomy (anticoagulant treatment, treatment with clopidogrel, coagulopathy or severe thrombocytopenia)
- Loss of polypectomy specimen
- Refusal to participate

Randomization

It will be done once the patient agrees to participate in the work and the first candidate polyp has been identified. Each patient will be randomized (regardless of the number of injuries per patient) in such a way that all lesions of each patient will be removed in the same way. It will be stratified by endoscopist, in such a way that each endoscopist will have its sequence of sealed randomization. Within each stratum a pure randomization will be carried out through a sequence generated by computer where the probability of belonging to each group will be 0.5. A total of 60 numbered sealed opaque envelopes will be available for each endoscopist that will be stored in the endoscopy room and will be opened consecutively as patients are included.

Intervention

Patients who meet the inclusion criteria and do not present any exclusion criteria (preendoscopic) will be invited to participate in the study. The informed consent will be completed according to the law 41/2002 of autonomy of the patient without it being altered the relationship with your doctor or any damage to your treatment.

1) Endoscopic act

The interventions will be carried out in each of the participating centers. The scans will be performed under sedation according to the protocols established in each center. Once the lesion is identified, the method of extirpation of the lesion will be randomized.

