The Access program (Microsoft Corporation, Redmond, WA USA) will be used for the realization of the database and the statistical analysis of them will be carried out through the STATA program (StataCorp, 2013. Stata Statistical Software: Release 13. College Station, TX: StataCorp LP). In the quantitative variables, the arithmetic mean and the standard deviation will be calculated (variables that do not follow a normal distribution according to the Kolmogorov-Smirnov test will be described with median, minimum, maximum and interquartile range), and the qualitative ones will be expressed as percentages and your 95% confidence intervals.

The analysis of the primary objective, the proportion of incomplete polypectomies in both groups will be compared by means of the z test of homogeneity without using the correction of Yates. The confidence interval of the difference between the two groups will also be estimated. The analysis will be carried out by intention to treat, regardless of the type of polypectomy performed and per protocol (assigning the lesions assigned to the group Cold that are extirpated with hot snare to the Hot group). To evaluate possible confounding factors (endoscopist, nurse, handle type, location ...), the STATA confound user command will be used, defining as a significant change that which conditions a change in the odds ratio greater than 10% with respect to the one obtained with the complete model. In case several models do not present differences greater than 10%, the most parsimonious will be chosen.

Within the secondary objectives, the proportion of complications in both groups will be verified by the de2 test. To evaluate the factors associated with incomplete polypectomies and those associated with failed cold polypectomy, multivariate logistic regression techniques will be used.

8. Ethical aspects

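### The trial is sized for equivalence within 7 points, but the primary analysis is a homogeneity test with no interval level or decision rule tied to that limit; the missing endoscopist term is a lesser point

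*Combined protocol and SAP*

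**What the plan says.** **Design.** Section 2 hypothesises similar proportions of incomplete polypectomies. Section 5 (Sample size) assumes 10% in both groups, an equivalence limit of 7%, α 5% and power 80%. This gives 315 lesions per group, raised to 394 (788 in total) for 20% losses.

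**Primary analysis.** Section 7 says the two proportions "will be compared by means of the z test of homogeneity without using the correction of Yates"; the Abstract says the same. Section 7 adds: "The confidence interval of the difference between the two groups will also be estimated". It gives that interval no level and does not mention the limit. The only level it names is for description: "the qualitative ones will be expressed as percentages and your 95% confidence intervals".

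**Allocation.** The Abstract states: "Randomization will be performed stratified by endoscopist". Section 5 (Randomization) makes the patient the randomised unit, with all of a patient's lesions removed by the same technique. Each endoscopist has 60 envelopes. "Within each stratum a pure randomization will be carried out", with probability 0.5 for each arm.

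**Endoscopist in the analysis.** Section 7: "To evaluate possible confounding factors (endoscopist, nurse, handle type, location ...), the STATA confound user command will be used". The criterion is a change of more than 10% in the odds ratio. "In case several models do not present differences greater than 10%, the most parsimonious will be chosen".

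**The concern.** The sample size and the primary analysis answer different questions. A homogeneity test asks whether the arms differ. The design asks whether any difference is smaller than 7 points. A non-significant z test does not answer the second question, and the interval that could answer it has neither a level nor a rule. An analyst could take 95%, the only level in section 7, and lose power that the sample size was meant to secure. The choice could also be made after the results are known.

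Two smaller points concern the same estimate. The stratification factor is absent from the primary test and interval, and the search in which it appears works on the odds-ratio scale, which cannot be read against a 7-point limit. And patients are randomised while lesions are counted as if independent.

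**Working it through.** **1. Reproducing 315 and 394.** Inputs from section 5: p = 0.10 in both arms, limit 0.07, α 0.05, power 0.80. For two one-sided 5% tests at a true difference of 0:

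n = 2p(1−p)(1.645 + 1.282)²/0.07² = 314.6, so 315 per group; 315/0.8 = 393.75, so 394.

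Other readings do not give 315:
- 2.5% per side (a 95% interval): 386
- non-inferiority: 228 (one-sided 5%) or 289 (2.5%)
- superiority, 10% v 17%: 373 (401 with continuity correction)
- superiority, 10% v 3%: 194

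So the limit is read as absolute, and the sample size implies a 90% interval.

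**2. Power by interval level.** SE = √(0.18/n), which is 0.0239 at 315 and 0.0214 at 394. Power = 2Φ(0.07/SE − z) − 1.

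| Evaluable per group | 90% interval | 95% interval |
|---|---|---|
| 315 | 80.1% | 66.7% |
| 394 | 89.7% | 81.1% |

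**3. What the z test would do.** At a true 10% v 17% with 315 per group, the pooled SE is √(2 × 0.135 × 0.865/315) = 0.0272 and the unpooled SE is √((0.09 + 0.1411)/315) = 0.0271. P(non-significant) = 1 − Φ((0.07 − 1.96 × 0.0272)/0.0271), about 27%; at 394 it is about 18%. Exact binomial enumeration gives 26% and 17%.

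With the 10% variance and 315 per group, the largest observed difference that meets the limit on a 90% interval is 0.07 − 1.645 × 0.0239 = 3.1 points. The z test stays non-significant up to about 1.96 × 0.0239 = 4.7 points. An observed difference between 3.1 and 4.7 points would be non-significant without showing equivalence.

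**4. Endoscopist.** Unblocked allocation does not secure balance within an endoscopist: a full set of 60 splits 24:36 or worse with probability 2 × P(Bin(60, 0.5) ≤ 24) = 15.5%.

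The documents give neither the number of endoscopists nor their spread, so both are assumed. Simulation: 630 lesions, one per patient, 10% incomplete, 90% interval, 15 equal endoscopists, 6,000 trials per setting, Mantel-Haenszel difference against crude.

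| Between-endoscopist SD (logit) | Power, stratified | Power, crude | Median gap between estimates (95th percentile), points |
|---|---|---|---|
| 0 | 79% | 80% | 0.2 (0.7) |
| 0.5 | 80% | 80% | 0.3 (1.0) |
| 0.8 | 82% | 80% | 0.4 (1.4) |
| 1.0 | 83% | 80% | 0.5 (1.6) |

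SD 0.5 puts the middle 80% of endoscopists at 5-16% incomplete; SD 1.0 puts them at 2-22%. At a true 7-point difference, the error rate was 5.0-5.6% crude and 5.0-5.4% stratified.

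With unequal volumes, 15 to 60 endoscopists, and those with fewer than 20 lesions pooled within centre, the change in power from stratifying was −1.3 to −1.8 points (SD 0), +0.1 to −1.0 (SD 0.5) and +1.0 to +3.1 (SD 1.0). With 60 equal strata left unpooled and SD 0, power fell from 80.0% to 74.5%.

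**5. Several lesions per patient.** Design effect DE = 1 + (m − 1) × ICC. Assume a mean m of 1.2 to 2.0 lesions per patient and an ICC of 0.05 to 0.30 (the documents give neither), so DE is 1.01 to 1.30.
- Error at the limit when clustering is ignored: 1 − Φ(1.645/√DE) = 5.1% to 7.5%.
- Power at 315 when it is allowed for: 79.6% down to 64.4%.
- Evaluable lesions needed: 315 × DE = 319 to 410 per group.

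**The case against.** The strongest reply is that the plan already holds what is needed. It states a limit and promises an interval of the difference, and a competent analyst would set one against the other. That is partly right: nothing in the documents says that a non-significant z test will be read as equivalence, so the 26% figure is the risk of that reading and not a forecast. But the test is named as the primary analysis, the interval has no level, and the level that fits the sample size differs from the only one section 7 mentions.

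A second reply is that 67% is the low end. This stands. The 20% loss allowance includes failed cold polypectomies, which the intention-to-treat analysis would keep, so evaluable numbers could lie anywhere from 315 towards 394. The fair range with a 95% interval is 67-81%.

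A third reply is that endoscopist adjustment is a preference: there is no consistent gain at SD 0.5 or below, and section 7 does name endoscopist as a possible confounder. This largely stands, which is why it is the secondary point. A reader might infer that stratified randomisation makes the unadjusted analysis invalid. The documents do not support that: allocation within strata is simple, and the simulated error rates stay close to 5%. Nor do they support the opposite inference, that the crude analysis is sound without qualification, because patients are randomised and lesions are counted.

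**Conclusion.** The concern holds, with most of its weight on the missing equivalence decision. The named primary test cannot deliver the conclusion for which the trial is sized, and leaving the interval level open moves power between 80% and 67% at 315 evaluable lesions per group, or between 90% and 81% at 394. These figures rest on the plan's own 10% rate, on the 7% limit being absolute, and on independent lesions.

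The endoscopist term is worth about 0 to 3 points of power, depending on an assumed spread, and costs about 1 to 2 points if endoscopists do not differ. Its other use is to correct chance imbalance: the two estimates can differ by 1 point or more against a passing threshold of 3.1, so the choice should be fixed beforehand. Patient clustering could matter more than endoscopist, but its size depends on lesions per patient and ICC, which the documents do not give.

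**What to change.** In section 7, before central pathology results are merged with allocation, replace the z test as the deciding analysis with:

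> Equivalence is concluded if the 90% confidence interval for the cold-minus-hot difference in the proportion of incomplete polypectomies lies within −7 to +7 percentage points, in both the intention-to-treat and per-protocol analyses. The difference is estimated by linear (risk-difference) regression on arm and endoscopist with standard errors clustered by patient. Endoscopists with few lesions are pooled within centre by a rule fixed in advance on lesion count only.

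The pooling rule should also say what happens when a centre's pooled total is still small. Report the crude difference as supportive, and label the 10% odds-ratio search exploratory. Make the Abstract agree.

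**Cost.** This is wording only; section 5 already collects endoscopist data. Adjustment costs about 1-2 points of power if endoscopists do not differ. Under the assumed clustering the standard error is √1.01 to √1.30 times as large (0.5% to 14% wider), which reflects uncertainty already present. In simulations of this regression with 15 endoscopists and an assumed 60/25/15% of patients having 1/2/3 lesions, the error rate at the limit was 5.0-6.0% (Monte Carlo SE 0.4 points). Requiring both analysis sets to pass can only lower power, by an amount that depends on how many lesions change group; this was not quantified.

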Assuming a proportion of incomplete polypectomies in both groups of 10% (using the taking of biopsies as a diagonostic pattern) and setting an equivalence limit of 7%, a total of 315 lesions per group are estimated to have an α risk of 5% and a power of 80%. Assuming a proportion of losses (polyps not recovered for histological study, polypectomies of the failed Cold group of 20%), an estimated 394 lesions per group are needed, with a total of 788 lesions in total.

Data Collect

All the variables concerning the characteristics of the endoscopist, the patient and the injuries included will be collected in each center. The variables related to the histological diagnosis will be collected in the same way in the respective center. The variables concerning the follow-up will be collected in a centralized manner, through a telephone call that will be made between 3 and 4 weeks from the procedure. The variable related to the histological study of the base of the polyp will be collected in a centralized manner by the pathologist in charge of the analysis of the samples.

6. Data management

Data from the data collection notebooks will be merged by the main researcher or collaborating researchers anonymously, encrypted and dissociated from the clinical information by means of a patient identification code (ID), in a database made through the program Access (Microsoft Corporation, Redmond, WA USA). A copy of the database will be used in each participating center, which will be merged after completing the data collection. The responsible researcher will define an ID for each participant. The data entered in the

database will be anonymous and the database will be protected with a password to which only the researchers will have access.

The unified file will be kept at the Río Hortega University Hospital and will be maintained until the end of the study. Regarding the application of the Organic Law on Data Protection 15/1999 and Royal Decree 1720/2007 that develops it, it should be noted that the protocol defined in the project oriented to epidemiological analysis, determines that the files will record information completely anonymized

7. Statistical analysis

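### Randomisation is presented as stratified by endoscopist, but unrestricted allocation within each stratum balances endoscopists no better than one simple list, and the primary test ignores endoscopist

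*Combined protocol and SAP*

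**What the plan says.** The Abstract announces the design feature: "Randomization will be performed stratified by endoscopist". Section 5 (Methods), Randomization, explains it: "It will be stratified by endoscopist, in such a way that each endoscopist will have its sequence of sealed randomization". The rule inside each stratum follows: "Within each stratum a pure randomization will be carried out through a sequence generated by computer". Every patient has the same one-half chance of either technique. On the envelopes the section says: "A total of 60 numbered sealed opaque envelopes will be available for each endoscopist". They are kept in the endoscopy room and opened in order. The patient is the unit of allocation, so that "all lesions of each patient will be removed in the same way". No block, urn, biased coin, minimisation or fixed 30:30 envelope set is described anywhere.

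Section 7 (Statistical analysis) compares the primary proportions with an unstratified z test and a confidence interval for the difference. Endoscopist appears there only as the first of several possible confounders, to be screened by whether the odds ratio changes by more than 10% from the full model.

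**The concern.** Stratification balances a factor only when allocation within each stratum is restricted. With independent 0.5 allocation, keeping a separate list for each endoscopist changes who holds the envelopes but not the distribution of the split.

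Endoscopist is a sensible factor to control. The same person performs the resection and takes the base biopsies that define the primary outcome, and the Introduction concedes that the biopsy method has a subjective element that depends on where samples are taken. If endoscopists differ in their rates of incomplete resection, uneven splits let part of that difference enter the crude contrast by chance. The primary analysis does not remove it: the z test ignores endoscopist, and the 10% screen is a data-dependent step separate from that test.

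**Working it through.** **Inputs from the documents.** Allocation probability 0.5 and at most 60 envelopes per endoscopist (section 5, Randomization). Incomplete polypectomy 10% in both groups, equivalence limit 7%, alpha 5%, power 80%, 315 evaluable lesions per group, 394 after 20% losses (section 5, Sample size).

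**Assumptions.** The number of endoscopists and the patients per endoscopist are not given, so every stratum size below 60 is a scenario. The spread of rates between endoscopists is not given either. Lesions are treated as independent.

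**1. The plan's sample size.** Two one-sided tests at 5% with 80% power give n = 2 × 0.1 × 0.9 × (1.645 + 1.282)² / 0.07² = 314.6, so 315 per group. Then 315 / 0.8 = 393.75, so 394 per group and 788 in total. The stated figures reproduce, and nothing in this point changes them.

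**2. Split within one endoscopist under the stated rule.** The number of Cold patients among k is Binomial(k, 0.5).

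| k | 95% range for Cold | Exact balance | 60:40 split or worse |
|---|---|---|---|
| 60 | 22 to 38 | 10.3% | 15.5% |
| 40 | 14 to 26 | 12.5% | 26.8% |
| 20 | 6 to 14 | 17.6% | 50.3% |
| 10 | 2 to 8 | 24.6% | 75.4% |

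**3. Separate lists against one list.** By simulation, assuming 13 endoscopists with 60 patients each, the mean absolute difference between arms within an endoscopist is 6.15 patients under both schemes. The chance that at least one endoscopist has a 36:24 split or worse is 0.89 with separate lists and 0.88 with one list, the same within simulation error.

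**4. Effect on the primary result.** The standard error of the crude difference is √(2 × 0.1 × 0.9 / 315) = 2.39 percentage points. If endoscopist rates have SD τ, perfect balance within endoscopists, with an analysis that uses it, would give √(2 × (0.09 − τ²) / 315).
- τ = 0.03: √(2 × 0.0891 / 315) = 2.38 points, a reduction of 0.5%.
- τ = 0.05: √(2 × 0.0875 / 315) = 2.36 points, a reduction of 1.4%.
- τ = 0.10: √(2 × 0.0800 / 315) = 2.25 points, a reduction of 5.7%.

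Simulated two-sided type I error of the crude z test under simple randomisation is about 5% for τ of 0.03 and 0.05 (13 endoscopists with 48 lesions each, assumed).

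**5. What permuted blocks would give and cost.** With blocks of 4, 6 and 8 the difference between arms within an endoscopist can never exceed 4 patients. But someone who always guesses the arm used less often so far is right about 68% of the time over a 60-envelope list, and about 65% with blocks of 8, 10 and 12. Under the stated rule the figure is 50%. The guesser does not need to know the block sizes, so concealing them does not lower these figures.

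**The case against.** Simple randomisation is a defensible choice here. The endoscopist is unblinded, has a personal list, sees every past allocation, and opens the envelope after judging that a first lesion of 5–9 mm is present. Unrestricted allocation keeps the next assignment unpredictable, and blocking would weaken that. Its chance imbalance is already covered by the variance of the crude test. Uneven splits are also cheap: 36:24 keeps 4 × 0.6 × 0.4 = 0.96 of the efficiency of an equal split. The plan never promises equal numbers within endoscopists, separate lists are a practical need when envelopes sit in several centres, and endoscopist is at least screened as a confounder.

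Most of this stands. It rules out a stronger reading that a reader might infer, namely that the missing restriction confounds technique with operator skill and biases the primary comparison. The documents do not support that: each patient has the same 0.5 chance whoever the operator is, so the contrast is unbiased in expectation and the test keeps its size. Nor does the plan give no balance at all; it gives balance in expectation, with none beyond chance.

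Two things remain. A scheme announced as stratified has no balancing effect from its strata. And the confounder screen is not a substitute, because it leaves the primary z test unadjusted and makes adjustment depend on the data.

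**Conclusion.** The point holds as a mismatch between the label and the rule, with a small cost in precision. Under the stated rule, a full 60-patient stratum can reasonably run from 22:38 to 38:22, and smaller strata can be proportionally more uneven. Against a 7-point limit, the standard error that could be saved is about 0.01 to 0.03 points out of 2.39 if endoscopist rates vary with an SD of 3 to 5 points, and about 0.14 points at an SD of 10. These sizes rest on the assumed spread and on independent lesions. The sample size is unaffected. The change is worth making because it is cheap and the plan itself chose endoscopist as its only stratification factor, not because the result would otherwise be invalid.

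**What to change.** **Main change, in section 7.** Make the primary estimate of the difference and its confidence interval stratified by or adjusted for endoscopist, for example with a Mantel-Haenszel risk difference, and specify this in advance in place of the 10% change-in-odds-ratio screen for this factor. It needs no extra patients and has no predictability cost. The remaining cost is that an endoscopist whose patients all fall in one arm adds nothing to the stratified estimate.

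**Optional, only if envelopes are not yet sealed.** Generate each list with permuted blocks of randomly varying, undisclosed size. This is one setting in the program that makes the lists. The protocol should state the downside: about 68% of allocations could be guessed with blocks of 4, 6 and 8, or about 65% with 8, 10 and 12, against 50% now.

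**If simple randomisation is kept for unpredictability.** Say so in the Abstract and in section 5, describe the lists as separate for each endoscopist, and do not present the scheme as balancing endoscopists.

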The evaluation of the resections can be done by several methods, which conditions the disparity observed in the different works. The ideal method would be the evaluation of the margins of lateral and vertical resection. However, this is complicated by the usual handling of the samples (fragmented samples, samples submitted for histological study in pot instead of mounted ...), so the number of non-valuable samples can reach 40% (11). Another option is to take biopsies from the edges of the lesion. Although it includes a component of subjectivity, depending on where the biopsies are taken, it allows to evaluate all the injuries. In 2010, Pohl et al published a paper based on data from 2 North American centers (12). All resections were made with hot loop, being incomplete in 6.8% of the lesions <10 mm. The cold loop technique presents similar results. In a study in which 59 slightly smaller polyps were analyzed (average size 3.7 mm), incomplete resections were observed in 6.8% (13). The studies in which the edges of resection are evaluated show greater proportions in both techniques. The work published in 2015 by Din and colleagues, comparing two techniques of cold cutting in lesions of 3-7 mm, observed a proportion of incomplete polypectomies close to 30% (14) while another retrospective observational work with 175 lesions of 3-10 mm extirpated with cold snare and 1010 of 6-15 mm excised with hot snare, the proportion of histologically complete polypectomies was 53% and 61%, respectively (15).

2. Hypothesis

Conceptual hypothesis:

Cold snare polypectomy presents a proportion of incomplete polypectomies similar to polypectomy with hot snare.

Operational hypothesis:

Two endoscopic techniques will be compared from two groups created by a random assignment to one or another type of polypectomy, evaluating the proportion of non-excised polypoid tissue after it. This will be done from random biopsies of the edges of the lesion and possible macroscopic remnants

3. Objectives.

Primary objective:

To compare the proportion of incomplete polypectomies in both types of polypectomy (cold snare vs. hot snare).

Secondary objectives:

- ²Compare the proportion of immediate and delayed bleeding complications, total and according to the severity that they present according to the ASGE classification.
- ² Compare the evolution of abdominal pain in the 5 hours postprocedure between both groups.

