- Cold Group: polypectomy with a cold snare will be carried out according to the usual standards recommended by international societies. As far as possible we will try to arrange the lesion in the position equivalent to 5 o'clock on the dial, the end of the snare will be placed several millimeters from the lesion and the tip of the catheter will be angled downwards as the Asa, without aspiration at any time to avoid entrapment of the submucosa.
- -Hot Group: polypectomy with snare connected to the electrosurgical unit according to the standards recommended by international societies, using a mixed current (cut-coagulation). Once the lesion is captured, the snare is pulled to slightly separate it from the surrounding mucosa before polypectomy. Elevation of the lesion prior to polypectomy will not be performed.
- -Common evaluation: once the polypectomies are completed, the basis of the polypectomies will be evaluated, taking biopsies from any suggestive area and also 2 random biopsies at the base of the polypectomy.

2) Postendoscopic follow-up

After a minimum of 21 days and a maximum of 28 days from the endoscopic examination, the patient will be contacted by telephone to collect the form about the evolution of the abdominal symptoms and to collect data about the appearance of complications (questions will be asked about visits to the hospital and in a targeted manner about the most frequent symptoms of the usual complications (fever, hemorrhage, abdominal pain).

3) Histological analysis

The analysis of the specimens of the polypectomies will be carried out in each center according to their usual protocol. The analysis of the biopsies of the base of the polyp will be carried out centrally by a pathologist with more than 5 years of experience in digestive pathology. Samples from the base of the polyp will be sent biweekly from each center to the university health care complex in Salamanca through a messenger service. The pathologist will be blinded regarding the histological diagnosis of the excised polyp and the type of polypectomy (although it is true that it is difficult to blind this last point since the presence of heat artifacts in those removed with a hot handle is very frequent). The samples sent for centralized analysis will not be conserved, but will be destroyed once the study is completed according to the usual protocols.

Sample size

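### Where the two random biopsies are taken is left to an operator who knows the arm, so a placement difference between arms could bias the primary comparison in either direction

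*Combined protocol and SAP*

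**What the plan says.** The Abstract defines the endpoint: "The primary objective is the proportion of incomplete polypectomies, which will be analyzed centrally from random biopsies of the edges of the lesion". The operational hypothesis in section 2 adds visible remnants: "This will be done from random biopsies of the edges of the lesion and possible macroscopic remnants". The working instruction is in section 5, Intervention, under Common evaluation: "taking biopsies from any suggestive area and also 2 random biopsies at the base of the polypectomy". So the first two places name the edges and the third names the base.

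The Introduction accepts the weakness of the method: "Although it includes a component of subjectivity, depending on where the biopsies are taken, it allows to evaluate all the injuries".

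On knowledge of the arm, section 5 (Randomization) has the envelopes "stored in the endoscopy room and will be opened consecutively as patients are included", and allocation is stratified by endoscopist. Under Histological analysis the central pathologist is blinded to technique, with this caveat: "it is difficult to blind this last point since the presence of heat artifacts in those removed with a hot handle is very frequent".

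Nothing in the text gives positions for the random biopsies, a device for choosing them, a separate operator or a record of the site.

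**The concern.** A site is random only if something other than the operator's judgement selects it. Here the person sampling has, on the natural reading, just done the resection, knows whether current was used and can see the base. If that person samples a clean-looking sector more often after one technique than after the other, the chance of finding residual tissue differs by arm.

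The safeguards in the plan do not reach this step. The pathologist's blinding begins after the tissue has been chosen. Stratifying by endoscopist balances each operator's general habits between arms, but not a habit that changes with the technique. Adjusting for endoscopist in the analysis cannot recover tissue that was never sampled.

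In an equivalence trial, lower detection in the arm with more residual tissue pulls the observed rates together and favours the conclusion the trial is designed to reach. Lower detection in one of two truly equal arms does the reverse and costs power.

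**Working it through.** **Inputs from the documents** (section 5, Sample size): incomplete rate 10% in both arms, stated as measured by biopsy; equivalence limit 7 points; α 5%; power 80%; 315 lesions per group, or 394 after 20% losses.

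**Reproducing the plan's figure.** Two one-sided 5% tests, unpooled variance:

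n = 2p(1−p)(z₀.₉₅ + z₀.₉₀)² / margin² = 2 × 0.10 × 0.90 × (1.645 + 1.282)² / 0.07² = 314.6, so 315.

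With losses, 315 / 0.80 = 393.75, so 394 per group and 788 in total. The sample size is not in question. The match also supports using two one-sided 5% tests below, although section 7 gives no level for the confidence interval.

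**Model.** Let r be detection in Cold relative to Hot. The documents give no value, so r is an assumption. Observed Cold rate = Cold rate × r. With n = 315, observed difference d (Cold minus Hot) and SE = √[(p_C(1−p_C) + p_H(1−p_H))/n],

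P(equivalence) = Φ((0.07 − d)/SE − 1.645) − Φ((−0.07 − d)/SE + 1.645).

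Lesions are treated as independent, and biopsies of suggestive areas are given no offsetting effect. That makes this the upper end.

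**A. A difference is hidden** (17% Cold, 10% Hot: exactly at the limit, both read as biopsy-measured):

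| r | Observed Cold | d | SE | P(equivalence) |
|---|---|---|---|---|
| 1 | 17.0% | 7.0 points | 2.71 points | 5% |
| 0.875 | 14.875% | 4.875 points | 2.62 points | 20% |
| 0.75 | 12.75% | 2.75 points | 2.53 points | 50% |

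**B. A difference is created** (10% in both arms): at r = 1, P(equivalence) is 80%. At r = 0.7 the observed Cold rate is 7%, d = −3 points, SE = 2.22 points, and P(equivalence) falls to 56%.

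**C. The opposite direction.** Keep 17% in Cold but lower detection in Hot to 0.875. The observed Hot rate is 8.75%, d = 8.25 points, SE = 2.65 points, and P(equivalence) drops to about 2%. The sign of the bias depends on which arm is under-sampled, and the documents do not say.

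**D. Partial offset from targeted biopsies.** Suppose targeted biopsies supply half of the measured positives in both arms (again an assumption). The effective ratio becomes 0.5 + 0.5r: 0.9375 for r = 0.875 and 0.875 for r = 0.75. P(equivalence) in A is then 11% and 20% instead of 20% and 50%.

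**The case against.** The strongest reply has four parts.

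*The random pair is not the whole endpoint.* Correct. A reader might infer that these two biopsies alone define incomplete polypectomy. They do not: suggestive areas and macroscopic remnants are sampled too, and part D shows that this can shrink the effect considerably. The offset is not guaranteed, because on the natural reading the same unblinded person decides what looks suggestive.

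*The figures can be overstated.* Correct. It is tempting to treat 17% and 10% as true rates and discount them for imperfect detection. Detection of 80% in both arms gives 13.6% against 8% and a 14% chance of equivalence; 70% Cold with 80% Hot gives 36%; 60% with 80% gives 67%. The documents do not support that reading, because Sample size already states the 10% as biopsy-measured. The step from 5% to 14% would in any case come from equal under-detection in both arms, which is not a placement difference.

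*Nothing shows that bias occurs, or which way.* Also correct. A reader might infer that the trial is tilted towards equivalence. No section supports that direction. The text does not even name who takes the biopsies. Stratification by endoscopist removes part of the problem.

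*The authors disclosed the subjectivity.* They did, as the price of being able to evaluate every lesion. Disclosing it does not control it, and the methods add no control. Annex 1 is not in the text provided; section 5 describes it as defining the variables to be collected, not a sampling procedure.

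What stands is the gap itself: undefined placement, an operator aware of the arm, and an endpoint that the protocol says depends on placement.

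**Conclusion.** The concern holds as a possibility that the design leaves open, and it is worth closing. The plan calls the two biopsies random without making them so, and it names two different sites. A placement difference between arms could move the comparison either way. Under the assumed ratios, and with no offset from targeted biopsies, the chance of declaring equivalence at a difference equal to the limit rises from 5% to 20% or 50%, and power under true equality falls from 80% to 56%. These are upper-end illustrations resting on assumed relative detection, independent lesions and two one-sided 5% tests. The size and direction in practice are unknown. No sample-size figure is wrong on this account, and more lesions would not remove the bias.

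**What to change.** In section 5, and consistently in the Abstract and section 2:

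1. Use one site term, edge or base, throughout. This has to be settled before positions can be assigned.
2. Assign the positions of the two random biopsies in advance and identically in both arms. They can be fixed opposite positions, or a computer-generated pair revealed only after the resection is finished. The sealed envelopes already prepared for each endoscopist show that the second option is practicable.
3. State the reference for 12 o'clock, for example relative to the lumen axis, so that rotating the scope does not change the assigned site.
4. Record the site sampled and any deviation, and tabulate deviations by arm.
5. Report random and targeted biopsy results separately by arm.

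The number of random biopsies stays at 2. No extra lesions or staff are needed; the cost is a few sentences, a recording field and, for the computer-generated option, one printed slip per patient. The downside is that some positions will be hard to reach and must be logged as deviations. The change needs to be in place before enrolment, because unrecorded sites cannot be reconstructed later.
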